7.1.2 Neurological Toxicities

In patients receiving blinatumomab in clinical trials, neurological toxicities have occurred in approximately 50% of patients. The median time to onset of any neurological toxicity was 7 days. Grade 3 or higher (severe, life-threatening, or fatal) neurological toxicities following initiation of blinatumomab administration occurred in approximately 15% of patients and included encephalopathy, convulsions, speech disorders, disturbances in consciousness, confusion and disorientation, and coordination and balance disorders. The majority of events resolved following interruption of blinatumomab, but some resulted in treatment discontinuation.

Subjects will be closely monitored for signs and symptoms of neurological toxicities, and interrupt or discontinue blinatumomab (see table 6-1).

7.1.3 Tumor Lysis Syndrome

Tumor lysis syndrome (TLS), which may be life-threatening or fatal, has been observed in patients receiving blinatumomab. Subjects with bulky disease defined as adenopathy >10cm on CT imaging or circulating disease \geq 15,000 circulating malignant cells/ mm³ will receive allopurinol 300mg BID beginning 24 hours prior to first infusion and for 30 days following beginning of treatment for prophylaxis of tumor lysis syndrome.

7.1.4 Effects on Ability to Drive and Use Machines

Due to the potential for neurologic events, including seizures, patients receiving blinatumomab are at risk for loss of consciousness. Subjects will be advised to refrain from driving and engaging in hazardous occupations or activities such as operating heavy or potentially dangerous machinery while blinatumomab is being administered.

7.2 Adverse Event Characteristics

- **CTCAE term (AE description) and grade:** The descriptions and grading scales found in the revised NCI Common Terminology Criteria for Adverse Events (CTCAE) version 4.0 will be utilized for AE reporting. All appropriate treatment areas should have access to a copy of the CTCAE version 4.0. A copy of the CTCAE version 4.0 can be downloaded from the CTEP web site
http://ctep.cancer.gov/protocolDevelopment/electronic_applications/ctc.htm.
- **For expedited reporting purposes only:**
 - AEs for the agent(s) that are listed above should be reported only if the adverse event varies in nature, intensity or frequency from the expected toxicity information which is provided.
 - Other AEs for the protocol that do not require expedited reporting are outlined in the next section (Expedited Adverse Event Reporting) under the sub-heading of Protocol-Specific Expedited Adverse Event Reporting Exclusions.
- **Attribution of the AE:**
 - Definite – The AE is *clearly related* to the study treatment.
 - Probable – The AE is *likely related* to the study treatment.
 - Possible – The AE *may be related* to the study treatment.
 - Unlikely – The AE is *doubtfully related* to the study treatment.
 - Unrelated – The AE is *clearly NOT related* to the study treatment.

7.3 Expedited Adverse Event Reporting

7.3.1 Investigators **must** report to the Overall PI any serious adverse event (SAE) that occurs after the initial dose of study treatment, during treatment, or within 30 days of the last dose of treatment on the local institutional SAE form.

7.3.2 DF/HCC Expedited Reporting Guidelines

Investigative sites within DF/HCC will report AEs directly to the DFCI Office for Human Research Studies (OHRHS) per the DFCI IRB reporting policy.

7.4 Expedited Reporting to the Food and Drug Administration (FDA)

The Overall PI, as study sponsor, will be responsible for all communications with the FDA. The Overall PI will report to the FDA, regardless of the site of occurrence, any serious adverse event that meets the FDA's criteria for expedited reporting following the reporting requirements and timelines set by the FDA.

7.5 Expedited Reporting to Hospital Risk Management

Participating investigators will report to their local Risk Management office any participant safety reports or sentinel events that require reporting according to institutional policy.

7.6 Routine Adverse Event Reporting

All Adverse Events **must** be reported in routine study data submissions to the Overall PI on the toxicity case report forms. **AEs reported through expedited processes (e.g., reported to the IRB, FDA, etc.) must also be reported in routine study data submissions.**

8. PHARMACEUTICAL INFORMATION

A list of the adverse events and potential risks associated with the investigational or other agents administered in this study can be found in Sections 2.2.6 and 7.1.

8.1 Blinatumomab

[figure not shown]
8.1.1 Description

Blinatumomab is a novel single-chain antibody derivative of the BiTE® class. It is designed to target CD19 expressed on malignant B cells. It was developed by genetic engineering from 2 distinct parental murine monoclonal antibodies (mAbs): HD37, which recognizes the pan-B cell antigen CD19; and L2K-07, which specifically binds the T-cell receptor (TCR)-associated

complex, CD3. The single-chain variable fragments (scFv) of these antibodies are linked to form 1 single polypeptide chain.

Blinatumomab is a recombinant non-glycosylated protein, consisting of 504 amino acids with a molecular weight of approximately 55 kDa. The CD19-binding region of blinatumomab is positioned at the amino terminus, while the CD3-binding region is at the carboxy terminus. The 2 scFv are joined by a flexible linker consisting of glycine/serine amino acid residues. The domain structure of blinatumomab is shown in Figure 8-1.

Figure 8-1. Domain Structure of Blinatumomab (AMG 103)

8.1.2 Form

Blinatumomab is supplied in 4 mL single-use glass injection vials as a sterile, preservative-free, white to off-white lyophilized powder for reconstitution and administration by IV infusion. The lyophilized product is manufactured in 38.5 mcg vials of blinatumomab. Each vial contains the additional excipients and buffers listed below, pH 7.0:

Lyophilized Vial Presentations		
Blinatumomab content		38.5 mcg
Citric acid monohydrate		3.68 mg
Lysine hydrochloride		25.55 mg
Trehalose dihydrate		105.0 mg
Polysorbate 80		0.70 mg

8.1.3 Storage and Stability

Both the blinatumomab lyophilized Drug Product and IV Solution Stabilizer vials must be stored at 2°C to 8°C (36°F to 46°F) in their original outer package to maintain product integrity and prevent exposure to light.

Reconstituted vials should not be stored for longer than 4 hours between 22°C and 27°C (72°F and 81°F) or longer than 24 hours between 2°C and 8°C (36°F and 46°F).

Blinatumomab solution for infusion must be administered at ambient temperature and must not be kept at ambient temperature more than 48 hours. For storage prior to administration, the prepared infusion solution must be kept at 2°C to 8°C (36°F to 46°F). The total storage and administration time must not exceed 8 days.

8.1.4 Compatibility

Blinatumomab will run through a dedicated central line and will not be combined with any additional agents.

8.1.5 Handling

Qualified personnel, familiar with procedures that minimize undue exposure to themselves and the environment, should undertake the preparation, handling, and safe disposal of the chemotherapeutic agent in a self-contained and protective environment.

8.1.6 Availability

Blinatumomab is an investigational agent and will be supplied free-of-charge from Amgen.

8.1.7 Preparation

To prepare blinatumomab for intravenous administration, the lyophilized powder is reconstituted with sterile Water for Injection (sWFI). The reconstituted solution is added to an infusion bag containing 0.9% NaCl primed with a product-specific stabilizer (IV Solution Stabilizer). The IV Solution Stabilizer functions to prevent adsorption of blinatumomab to surfaces of the infusion components.

The IV Solution Stabilizer is supplied in 10 mL single-use glass injection vials as a sterile, preservative-free, clear, colorless-to-slightly-yellow liquid concentrate. It consists of 25 mM citric acid monohydrate, 1.25 M L-lysine hydrochloride, and 0.1% (weight/volume [w/v]) polysorbate 80, pH 7. Following dilution in 0.9% NaCl, the ingredient concentrations are 25 mM L-lysine hydrochloride, 0.002% (w/v) polysorbate 80, and 0.5 mM citric acid monohydrate..

8.1.8 Administration

Subjects will receive premedication with dexamethasone 20 mg (or equivalent) intravenously 1 hour prior to the first dose of blinatumomab of each cycle, prior to a step dose (such as Cycle 1 day 8), or when restarting an infusion after an interruption of 4 or more hours. Blinatumomab will be administered as a continuous IV infusion through a central venous catheter at a constant flow rate using an infusion pump for a 42 day cycle. Blinatumomab will start with a 7 day infusion at 9mcg/d. If no dose limiting toxicity (table 6.1) after 7 days, the dose will be escalated to 28 mcg/d for 7 additional days. If no dose limiting toxicity (table 6.1) after 14 days, blinatumomab will be infused at a target dose of at 112mcg/d for 28 days.

Blinatumomab solution for infusion may be administered using IV bags and infusion lines made of polyolefin/polyethylene, ethylene vinyl acetate (EVA), or PVC non-DEHP. Infusion lines with an in-line 0.2 μ m filter should be used.

8.1.9 Ordering

Blinatumomab will be provided by Amgen.

8.1.10 Accountability

The investigator, or a responsible party designated by the investigator, should maintain a careful record of the inventory and disposition of the agent using the NCI Drug Accountability Record Form (DARF) or another comparable drug accountability form. (See the NCI Investigator's Handbook for Procedures for Drug Accountability and Storage.)

8.1.11 Destruction and Return

At the end of the study, unused supplies of blinatumomab should be returned to Amgen or destroyed according to institutional policies. Destruction will be documented in the Drug Accountability Record Form.

9. BIOMARKER, CORRELATIVE, AND SPECIAL STUDIES

9.1 Correlation of Response and CNS Toxicity With B:T Lymphocytes Ratio In Peripheral Blood Collection of Specimen(S).

A baseline B cell to T cell (B:T) ratio in peripheral blood at or below 1:10 has been identified as a predictive factor for occurrence of neurological AEs.(13) We will correlate baseline B cell to T cell (B:T) ratio in peripheral blood measured by flow cytometry with neurologic events in a descriptive manner. Flow cytometry will be performed at the enrolling institution per standard protocol.

10. STUDY CALENDAR

10.1 Pre-Treatment Evaluations -within 45 days of the start of protocol therapy, unless otherwise noted

- Signed informed consent document
- Vital signs, including height, weight, temperature, pulse, blood pressure, respiratory rate, and oxygen saturation
- Complete physical examination
- Medical history: Detailed documentation of disease and treatment history with outcomes.
- ECOG performance status
- Concurrent medical conditions.
- Concurrent medications within 30 days of C1D1
- CBC with differential.
- Serum chemistries: Electrolytes (sodium, potassium, chloride, and bicarbonate), calcium, magnesium, phosphate, blood urea nitrogen (BUN), creatinine, glucose, beta-2 microglobulin, lactate dehydrogenase (LDH) and liver function tests (aspartate aminotransferase (AST) and alanine aminotransferase (ALT), alkaline phosphatase (ALP), total protein, albumin, and total bilirubin).
- Coagulation studies including prothrombin time and partial thromboplastin time
- HBsAg, HBsAb, HBcAb, and HCV Ab. HBV DNA PCR in patients who are HBsAg negative but who are HBcAb positive. *Hepatitis serologies may have been performed any time within one year of protocol enrollment.*
- Full body CT (neck, chest, abdomen/pelvis) and full body PET scan (or preferably a single combined-modality PET-CT scan). Bi-dimensional measurement of up to 3 of the largest target lesions. *Scans must be performed within 30 days of initiation of therapy.*
- Measurements will be made by the DF/HCC tumor imaging metric core (TIMC)
- Paraffin-embedded tissue block from diagnostic biopsy specimen will be obtained when available for performance of correlative testing. If the paraffin embedded block cannot be obtained, then 6 unstained slides will be obtained, if available. Patients without available specimens will still be eligible for study.
- Serum pregnancy test –All females of childbearing potential should complete a serum pregnancy test within 7 days prior to the administration of blinatumomab on day 1 of cycle 1. The test will be repeated on day 1 of cycle 2.
- Baseline flow cytometry for B:T cell ratio

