3.1.5 ECOG performance status ≤ 2 (see Appendix A)

3.1.6 Participants must have adequate organ and marrow function as defined below:

– absolute neutrophil count	$\geq 750/\text{mcL}$
– platelets	$\geq 75,000/\text{mcL}$
– total bilirubin	$< 2.0 \times$ upper limit of normal (ULN)
– AST(SGOT)/ALT(SGPT)	$\leq 2.5 \times$ institutional upper limit of normal or $\leq 5 \times$ ULN – if due to lymphoma infiltration
– creatinine	$\leq 2.0 \times$ ULN

OR

– creatinine clearance	$\geq 50 \text{ mL/min}/1.73 \text{ m}^2$ for participants with creatinine levels above $2.0 \times$ ULN .
------------------------	--

3.1.7 Ability to understand and the willingness to sign a written informed consent document.

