3.2 Exclusion Criteria

- 3.2.1 Participants who have had chemotherapy within 3 weeks, rituximab or obinutuzumab within 4 weeks, or radioimmunotherapy within 6 weeks prior to entering the study, or those who have not recovered from adverse events due to agents administered more than 3 weeks earlier. Subjects actively progressing within that window who have recovered from toxicities of prior therapy are also eligible.
- 3.2.2 Autologous stem cell transplantation within 12 weeks prior to study entry
- 3.2.3 Prior allogeneic transplant
- 3.2.4 Therapeutic doses of corticosteroids within 14 days prior to study entry, defined as >20mg/day pf prednisone, or equivalent. Topical and/or inhaled steroids are permitted.
- 3.2.5 Participants who are receiving any other investigational agents.
- 3.2.6 Participants with known brain metastases should be excluded from this clinical trial because of their poor prognosis and because they often develop progressive neurologic dysfunction that would confound the evaluation of neurologic and other adverse events.
- 3.2.7 History of allergic reactions attributed to compounds of similar chemical or biologic composition to blinatumomab
- 3.2.8 Subjects with known HIV infection
- 3.2.9 Pregnant or lactating subjects.
- 3.2.10 Chronic infection with hepatitis B or hepatitis C virus
- 3.2.11 History of or current relevant CNS pathology such as epilepsy, seizure, paresis, aphasia, apoplexia, severe brain injuries, cerebellar disease, organic brain syndrome, psychosis
- 3.2.12 Prior history of another malignancy (except for non-melanoma skin cancer, *in situ* cervical or breast cancer, or localized prostate cancer) unless disease free for at least one year and felt at low risk of relapse by treating physician.
- 3.2.13 Uncontrolled intercurrent illness including, but not limited to, ongoing or uncontrolled systemic fungal, bacterial, viral, or other infection, symptomatic congestive heart failure, unstable angina pectoris, cardiac arrhythmia, or psychiatric illness/social situations that would limit compliance with study requirements.

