10.4 End of study evaluations

When a patient is removed from study, end of study assessments are to be performed within 30 days (+/- 2 days). If the patient is not available, the reason for not completing the end of study assessments must be recorded in the patient's source documents.

The following clinical assessments will be performed:

- Full physical examination
- Weight and vital signs (blood pressure, pulse rate, respiratory rate, oxygen saturation, and temperature)
- ECOG Performance Status
- Recording of AEs
- Recording of concomitant medications

The following laboratory assessments will be performed:

- CBC with differential and platelet count
- Serum chemistries: Na, K, Cl, HCO₃, glucose, blood urea nitrogen (BUN), creatinine, calcium, magnesium, phosphate, total bilirubin, AST, ALT, alkaline phosphatase, albumin, and total protein

Patients will be followed for 1 year after the last cycle of therapy for toxicity and duration of response (if applicable). The following procedures will be completed:

- Recording of AEs (patients and/or family members will be instructed to telephone the site with any changes in mental or physical status) for 90 days following their last dose of blinatumomab.

Visit evaluation schedule

1. Baseline evaluations must be performed \leq 45 days prior to cycle 1 administration of blinatumomab, unless otherwise stated.
2. Physical examination, vital signs, weight, height – Physical examinations, vital signs, and weight will be performed on the scheduled day, even if study medication is being held. More frequent examinations may be performed at the investigator's discretion, if medically indicated. If these baseline examinations were performed \leq 72 hours prior to the first dose of blinatumomab, they need not be repeated on day 1 of cycle 1. Vital signs (weight, temperature, respiratory rate, oxygen saturation, sitting blood pressure, and sitting pulse) should be performed weekly unless otherwise indicated. .
3. ECOG performance status –Assessment of ECOG Performance Status will be performed on the scheduled day, even if study medication is being held. More frequent examinations may be performed at the investigator's discretion, if medically indicated. If the baseline assessment was performed \leq 72 hours prior to the first dose of blinatumomab, then it does not need to be repeated on day 1 of cycle 1.

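### The blood tests that establish organ and marrow eligibility may be up to 45 days old at first dose, so they can predate the last permitted chemotherapy by up to 24 days, and no laboratory result is required before the infusion starts

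*Combined protocol and SAP*

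**What the plan says.** Section 10.1 sets the general rule for baseline tests: "Pre-Treatment Evaluations -within 45 days of the start of protocol therapy, unless otherwise noted". Note 1 of the visit evaluation schedule, printed under Section 10.4, repeats it: no more than 45 "days prior to cycle 1 administration of blinatumomab, unless otherwise stated".

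Three items in Section 10.1 have their own limits:
- Imaging: "Scans must be performed within 30 days of initiation of therapy".
- Pregnancy: "serum pregnancy test within 7 days prior to the administration of blinatumomab on day 1 of cycle 1".
- Hepatitis: "Hepatitis serologies may have been performed any time within one year of protocol enrollment".

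The entry for "CBC with differential" and the entry for serum chemistries have none, so the 45 days apply to both.

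These tests carry the eligibility decision. Section 3.1.6 says "Participants must have adequate organ and marrow function as defined below" and lists limits for neutrophils, platelets, bilirubin, AST/ALT and creatinine, with no date attached.

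Section 3.2.1 excludes "Participants who have had chemotherapy within 3 weeks, rituximab or obinutuzumab within 4 weeks, or radioimmunotherapy within 6 weeks prior to entering the study". It also excludes subjects with unresolved adverse events from earlier agents. It readmits subjects whose lymphoma is progressing inside the washout, provided they have recovered from the toxicity of that treatment. Section 3.2.2 sets 12 weeks for autologous transplant.

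Section 11.4, on measurable disease, states a different limit: baseline evaluations are not to be more than 4 weeks old when treatment begins.

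**The concern.** The limits in Section 3.1.6 are there to describe the subject who is about to receive the drug. A test window longer than a washout allows this order of events: blood drawn and found adequate, then a further dose of prior therapy, then the washout, then blinatumomab. The values on file would then say nothing about the effect of that last treatment on marrow, liver or kidney.

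Two things are at stake. One is subject safety at first dose. The other is the baseline against which early laboratory toxicity is judged. Table 6-1 acts on toxicity attributed definitely or possibly to the study drug. In its row for reactions other than cytokine release and neurologic events, a grade 3 event at 9 mcg/day, the first-week dose, leads to permanent discontinuation, and a grade 4 event leads to removal from study. Section 13.1 lists discontinuation for toxicity as a secondary safety endpoint. An abnormality carried over from prior treatment, first seen on a week 1 test without a current baseline, could be counted there.

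**Working it through.** **The plan's own figures.** The plan gives no calculation on this point. Its only calculated design figures are those of the two-stage design in Section 13.2 (6 or more of 13 to continue, then 15 or more of 28, at 40% and 65%). Exact binomial sums reproduce them: type I error 0.0930 (stated 0.093), power 0.9035 (stated 0.904), early stopping 0.574 and 0.046 (stated 0.57 and 0.05). None of these takes the laboratory window as an input.

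**Inputs.**
- L, the maximum age of the laboratory tests at first dose: 45 days (Section 10.1 and visit schedule note 1), or 28 days if Section 11.4 governs.
- w, the washout counted back from study entry: chemotherapy 21 days, rituximab or obinutuzumab 28, radioimmunotherapy 42 (Section 3.2.1), autologous transplant 84 (Section 3.2.2).
- g, the days from study entry to first dose. The documents do not give it. I assume 0, 7 and 14 to show the range.

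**Formula.** The oldest permitted test is on day -L. The latest permitted prior treatment is on day -(w + g). The test can predate that treatment by at most L - w - g days. Zero or less means no overlap.

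**Results at g = 0.**

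| Prior treatment | L = 45 | L = 28 |
|---|---|---|
| Chemotherapy | 45 - 21 = 24 | 28 - 21 = 7 |
| Rituximab or obinutuzumab | 45 - 28 = 17 | 28 - 28 = 0 |
| Radioimmunotherapy | 45 - 42 = 3 | 28 - 42 = -14 |
| Autologous transplant | 45 - 84 = -39 | 28 - 84 = -56 |

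**Sensitivity to g, chemotherapy.** With L = 45: 24 days at g = 0, 17 at g = 7, 10 at g = 14. With L = 28: 7 days at g = 0 and 28 - 21 - 7 = 0 at g = 7.

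**Does any other rule force a current test before dosing?**
- Visit schedule notes 2 and 3 effectively require the physical examination, vital signs, weight and performance status to be no more than 72 hours old at first dose, or repeated on day 1. Notes 5 and 7, on hematology and biochemistry, have no such rule.
- Section 10.2.1 and the same notes 5 and 7 call for weekly tests in cycles 1 and 2. A draw may fall on day 1, but nothing says it precedes the infusion, that its result must be seen first, or that the Section 3.1.6 limits must be met again.
- Section 4.1 has an investigator confirm eligibility. That check is against Section 3.1.6, which values inside the 45-day window satisfy.
- The recovery conditions in Section 3.2.1 name no test, threshold or date.

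So for chemotherapy and anti-CD20 antibody the order of events described above is within the rules as written.

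**The case against.** The strongest reply is that Section 3.2.1 already requires recovery. Subjects with unresolved adverse events from earlier agents are excluded, and the exception for progressing subjects is open only to those who have recovered. Blood drawn before a treatment cannot show recovery from it, so a careful investigator would repeat the test. This has real force. A reader might infer that the exception stretches the gap to the full 45 days. The documents do not support relying on that figure, because the exception's own condition points the other way. What stands against the reply is that recovery is tied to no dated laboratory result.

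Second, Section 10.1 defers to other stated limits, and Section 11.4 gives 4 weeks for all baseline evaluations. On that reading the chemotherapy gap is 7 days and the others close. But the sentence sits among rules for measuring lesions, so whether it reaches blood tests is unclear, and taken literally it contradicts the 45 days.

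Third, a reader might infer that leftover cytopenia would be blamed on blinatumomab and so corrupt the safety endpoint. The documents show only that this could happen. Section 7.2 offers five attribution levels, including unlikely and unrelated; the last row of Table 6-1 is confined to clinically relevant reactions; and treatment history is recorded in detail at baseline.

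Fourth, a reader might take the grade 3 or higher rates in Table 2-4 (neutropenia 12.6%, thrombocytopenia 11.6% in the NHL studies) as the size of the problem. They are rates on drug in earlier studies and say nothing about how many subjects would start below the limits here. The text introducing that table also notes that one study's rule to report all laboratory abnormalities may partly explain the higher thrombocytopenia rate.

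**Conclusion.** The point holds as a gap in the schedule. The 45 days are a stated rule, and they let the qualifying values predate the last chemotherapy by up to 24 days and the last anti-CD20 dose by up to 17. Those maxima assume that entry and first dose coincide and that the 45-day window governs. Each day between entry and first dose removes one day. The excess is 3 days at most for radioimmunotherapy, and autologous transplant is not affected, so the window is not longer than every washout.

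The consequence is a possibility. A subject could start below the limits in Section 3.1.6, and a residual abnormality could be attributed to the drug. The documents give no basis for a frequency. For scale only, one subject wrongly counted as discontinuing for toxicity would move that rate by 1/28 = 3.6 percentage points in the full sample. The calculated type I error and power do not change. The repair is worth making because it protects subjects at first dose and costs little.

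**What to change.** In Section 10.1 and the visit evaluation schedule, state that the blood count and chemistries used to establish Section 3.1.6 are drawn after the last prior anti-lymphoma treatment and within a short window before first dose, the length to be chosen by the sponsor. A cycle 1 day 1 sample can serve if its result is available before the infusion starts. State that the same dated tests support the recovery conditions in Section 3.2.1. Reconcile the 45 days in Section 10.1 and visit schedule note 1 with the 4 weeks in Section 11.4, and say which evaluations each limit covers.

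The cost is calendar wording and at most one repeat routine draw per subject. A few subjects may be delayed or fail screening on the newer values.
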